4 SAMPLE SIZE

Approximately 210 subjects are planned to be randomized at a 2:1 ratio into two treatment arms (approximately 140 subjects in the VERU-111 treated group and approximately 70 subjects in the Placebo treated group).

5 RANDOMIZATION

Controlled Quality Management Document		
	Sponsor:	Veru Inc.
	Protocol Number:	V3011902
STATISTICAL ANALYSIS PLAN. PHASE 2-3-4		

Randomization will be stratified by baseline WHO Ordinal Scale score of 4, 5 and 6 such that subjects with a WHO Ordinal Scale of 4, 5 and 6 at baseline are approximately equally distributed between the treatment groups.

6 PLANNED ANALYSES

No statistical analysis plan (SAP) prepared in advance of the data can be absolutely definitive and the final Clinical Study Report (CSR) may contain additional tables or statistical tests if warranted by the data obtained. The justification for any such additional analyses will be fully documented in the final CSR.

6.1 Analysis Sets

Subjects excluded from the analysis sets and the reason for their exclusion will be summarized and listed.

6.1.1 Enrolled Set

All subjects who gave informed consent.

6.1.2 Intent-to-Treat (ITT) Analysis Set

All randomized subjects will be included in this analysis set.

6.1.3 Modified Intent-to-Treat (mITT) Analysis Set

All randomized subjects who completed the efficacy portion of the trial and who do not have any major protocol violations will be included in the mITT Analysis Set. Subjects who were randomized but did not receive study medication will be excluded from the mITT Analysis Set.

All protocol deviations will be assessed and documented on a case-by-case basis before the database lock, and deviations considered to have a serious impact on the efficacy results will lead to the relevant subject being excluded from the mITT. Exclusion of subjects who were randomized using incorrect WHO scores will be evaluated. Also, exclusion of subjects who were randomized under original protocol (WHO strata 5 and 6) will be evaluated.

Before database lock, potential subject exclusions from mITT will be reviewed by the Sponsor and documented in a subject evaluability document.

Controlled Quality Management Document		
	Sponsor:	Veru Inc.
	Protocol Number:	V3011902
STATISTICAL ANALYSIS PLAN. PHASE 2-3-4		

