## 9.2 Analysis Sets

**Intent-to-Treat (ITT) population:** All randomized subjects will be included in this population.

**Modified Intent-to-Treat (mITT) analysis set:** All randomized subjects who do not have any major protocol violations will be included in the mITT population.

**Safety (SAF) analysis set:** All randomized subjects who received at least one dose of study medication (VERU-111 or Placebo) will be included in this population. The SAF population will be used as the safety population.

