6.11.3 Secondary Analyses for the Primary Endpoint

The primary endpoint, mortality rate at Day 60, will also be assessed in the subset of mITT patients and Safety Analysis Set (all treated subjects).

Additionally, similar analysis to primary analysis will be performed in subgroups for region, standard of care, WHO Ordinal Scale at baseline and vaccination status.

To obtain risk differences between treatment groups, the same analysis as described above for primary efficacy analysis will be performed except identity link function will be used. Example SAS code is as follows:

```
proc genmod data=a order=internal;
class treatment sex site remdesivir dexamethasone whostrata;
model response=treatment sex site remdesivir dexamethasone whostrata
  / type3 dist=bin link=identity;
lsmeans treatment / e diff exp cl;
run;
```

Additionally, mortality rates will be summarized using Kaplan-Meier (KM) survival curves and equality of treatment groups will be tested using log-rank test. Hazard ratios will be calculated using the Cox proportional hazards model including terms for treatment, gender, study site (or country or region), remdesivir use (No/Yes), dexamethasone use (No/Yes) and WHO Ordinal Scale strata used in randomization. Any subjects for whom survival status is not available at day 60 will be censored at the day of their last observed assessment or last captured event.

Example SAS code for log-rank test is as follows:

```
proc lifetest data=XXX outsurv=surv1
  plots=survival(atrisk=0 to 60 by 1);
time time*cens(1);
strata treatment;
run;
```

Example SAS code for proportional hazards model is as follows:

```
proc phreg data=XXX;
class treatment sex site remdesivir dexamethasone whostrata;
model time*cens(1)=treatment sex site remdesivir dexamethasone
  whostrata;
```

Controlled Quality Management Document		
	Sponsor:	Veru Inc.
	Protocol Number:	V3011902

```
hazardratio treatment;  
assess ph / resample seed=1234;  
run;
```

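### The SAP's mITT set departs from the protocol by adding an undefined completion condition and open-ended exclusions to a set used to re-analyse Day-60 mortality

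*SAP*

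**What the plan says.** Protocol 9.2 gives a one-condition definition: "All randomized subjects who do not have any major protocol violations will be included in the mITT population".

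SAP 6.1.3 starts from a narrower set: "All randomized subjects who completed the efficacy portion of the trial and who do not have any major protocol violations". It then adds:

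- a treated-only rule: "Subjects who were randomized but did not receive study medication will be excluded from the mITT Analysis Set";
- an open question on stratification errors: "Exclusion of subjects who were randomized using incorrect WHO scores will be evaluated";
- an open question on early entrants: "exclusion of subjects who were randomized under original protocol (WHO strata 5 and 6) will be evaluated";
- a case-by-case rule under which "deviations considered to have a serious impact on the efficacy results will lead to the relevant subject being excluded from the mITT".

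The decisions are taken before database lock: "potential subject exclusions from mITT will be reviewed by the Sponsor and documented in a subject evaluability document".

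The set has a stated use. Under SAP 6.11.3 the primary endpoint "will also be assessed in the subset of mITT patients and Safety Analysis Set". Protocol 9.4.2 plans the same mITT analysis, and SAP 11.1 gives it Tables 14.2.1.5 and 14.2.1.6.

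SAP section 9, which records departures from the protocol's analyses, has three entries: the randomization strata, the WHO-score analysis and the Holm procedure. The mITT definition is not among them.

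**The concern.** Completing follow-up happens after randomization and can depend on treatment and on outcome. In a mortality trial the plan must say whether a subject who dies has completed, and SAP 6.1.3 does not. It also does not define the efficacy portion. Protocol 5.2 runs efficacy follow-up to Day 60, and Protocol 9.7.2, on the timing of the interim analysis, lists reaching Day 60, dying and withdrawing as separate events.

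The two optional exclusions are a different problem. They concern randomized subjects, and the SAP gives no rule for deciding. Entry under an earlier protocol version is not in itself a violation, and Protocol 6.2.1 still admits WHO scores 5 and 6. Protocol 3.3 reports that all seven Phase 2 deaths were in subjects with a baseline score of at least 5, so the subjects in question come from the strata where deaths are expected.

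At stake is whether the mITT mortality result can support the primary result. It cannot do so well if its membership rule conflicts with the protocol or is settled later on unstated criteria.

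**Working it through.** **1. Planning figures.** SAP 6.1.3 contains no number to reproduce. The inputs are from Protocol 9.1: 140 and 70 subjects, with mortality of 5% on VERU-111 and 25% on placebo. As a check, SE = √(0.05×0.95/140 + 0.25×0.75/70) = 0.0549, and −0.20 ± 1.96×0.0549 gives −0.308 to −0.092, the protocol's interval. The planned odds ratio is (0.05/0.95)/(0.25/0.75) = 0.158 and the risk ratio is 0.05/0.25 = 0.20.

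**2. Literal reading: death is non-completion.** Expected deaths are 140×0.05 + 70×0.25 = 7 + 17.5 = 24.5. All leave the set. Mortality is 0% in both arms and there is nothing to compare.

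**3. Other reading: death is completion.** Subjects whose Day-60 status is unknown still leave. SAP 6.11.1 imputes these subjects in the primary analysis, so the mITT analysis becomes complete-case. The documents give no loss rate, so the fractions below are assumptions.

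*Equal loss, 5% of each arm, all in fact alive.* VERU-111 becomes 7/133 = 5.26% and placebo 17.5/66.5 = 26.3%.

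| | No loss | 5% loss per arm |
|---|---|---|
| Risk ratio | 0.20 | 0.20 |
| Odds ratio | 0.158 | (7/126)/(17.5/49) = 0.156 |
| Risk difference | −0.200 | 0.0526 − 0.2632 = −0.211 |

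*Loss unrelated to outcome, 10% of each arm.* The odds ratio stays at 0.158. Power (pooled z-test, two-sided 0.05) goes from 97.5% to 96.2%.

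*Loss that differs by arm and outcome.* Take no true effect, with 25% mortality in both arms: 35 deaths and 105 survivors on VERU-111, 17.5 and 52.5 on placebo. Suppose a fraction f of VERU-111 deaths is dropped and nobody else. The odds ratio is then [35(1−f)/105]/(17.5/52.5) = 1−f. The rejection probability is Φ((|D|−1.96·SE₀)/SE₁) + Φ((−|D|−1.96·SE₀)/SE₁), where D is the risk difference, SE₀ the pooled and SE₁ the unpooled standard error. For f = 20% (7 subjects), D = 28/133 − 0.25 = −0.0395, SE₀ = 0.0616 and SE₁ = 0.0627, which gives 0.103.

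| f | Odds ratio | Rejection rate (nominal 5%) |
|---|---|---|
| 10% | 0.90 | about 6% |
| 20% | 0.80 | about 10% |
| 30% | 0.70 | about 18% |
| 50% | 0.50 | about 46% |

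These rows show sensitivity to one-sided loss. They do not forecast what will happen in this trial.

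**4. Optional exclusions.** Protocol version at entry is fixed before randomization, so removing that cohort does not select on outcome. It does remove randomized subjects from WHO strata 5 and 6. Their number is not given, so the effect cannot be sized. For mis-stratified subjects, the primary model in SAP 6.11.1 already adjusts for the stratum used in randomization. Only their mITT membership is open.

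**The case against.** A reader might infer that the set is selected on its outcome and that the mITT mortality analysis will have no deaths. The documents do not establish that. Protocol 9.7.2 concerns interim timing and does not define the SAP's term. Tables 14.2.1.5 and 14.2.1.6 plan the proportion alive, and its logistic regression, in this set, which presupposes that deaths are in it. An empty analysis would also be noticed at once. This part of the objection stands: the literal reading shows that the sentence is badly worded, not what the sponsor intends.

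A reader might also take the original-protocol option as selection on outcome. It is not, because it depends on a pre-randomization fact, and the SAP commits only to considering it.

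There are safeguards. The trial is double-blind (Protocol 7.1), the sponsor stays blinded at the interim (Protocol 9.7.2), and exclusions are documented before database lock. Protocol 8.10 seeks vital status by telephone or public records, so few subjects may be lost. The protocol's own definition also conditions on violations that may arise after randomization, so restoring it does not remove all selection. All this stands and limits the size of the problem.

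It does not answer the core point. The definition conflicts with the protocol, the completion condition causes trouble on either reading, SAP 6.1.3 does not state that the review of exclusions is blinded, and section 9 is silent.

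**Conclusion.** Wrong as written. SAP 6.1.3 departs from Protocol 9.2 by adding a completion condition, a treated-only condition and two exclusions without a criterion, and section 9 records none of them. The completion condition either removes all 24.5 expected deaths or makes the analysis complete-case. On the second and more plausible reading, an equal 5% loss hardly changes the treatment effect. Material bias needs loss that differs by arm or outcome, and the documents give no figures from which to judge how likely that is.

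The reach is limited to the secondary mITT analysis of Day-60 mortality. The primary analysis (SAP 6.11.1) uses ITT with multiple imputation, and the gate to the key secondary endpoints (SAP 6.11.7) uses the ITT result. It would be wrong to infer that the primary conclusion or the type I error control is affected. The 24.5 rests on the planning rates; the loss fractions are assumptions.

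**What to change.** In SAP 6.1.3:

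- Delete the completion condition, which restores the protocol's definition in that respect. Alternatively, state that death counts as completion and that loss to follow-up does not exclude.
- Do not treat entry under the original protocol as grounds for exclusion. If the sponsor wants such a rule, fix it now, before unblinding.
- Keep mis-stratified subjects in the set, under their randomized stratum as in the primary model.
- State that the review of the remaining deviations is blinded to treatment.

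In SAP section 9, list the treated-only condition as a change from the protocol. In SAP 11.1, correct the title of Table 14.1.1.6, which refers to a per-protocol set that section 6.1 does not define.

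The cost is SAP wording. No new data are needed, and the sample size and the primary analysis do not change.

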6.1.4 Safety (SAF) Analysis Set

All randomized subjects who received at least one dose of study medication (VERU-111 or Placebo) will be included in this analysis set.

6.2 Derived Data

This section describes the derivations required for statistical analysis. Unless otherwise stated, variables derived in the source data will not be re-calculated.

6.2.1 Baseline

The Day 1 visit assessment will serve as the baseline assessments.

6.2.2 Duration / Study Day / Time

Study day will be calculated as the number of days from first dose of study drug.

- date of event – date of first dose of study drug + 1, for events on or after first dose
- date of event – date of first dose of study drug, for events before first dose.

If subject does not get study drug then 'Day 1' visit date (or randomization date) can be used instead of the date of first dose of study drug.

6.2.3 Conventions for Missing and Partial Dates

All rules explained below for partial / missing dates will be followed unless contradicted by any other data recorded on the electronic Case Report Form (eCRF).

All dates presented in the individual subject listings will be as recorded on the eCRF (i.e., not completed as per the below rules).

6.2.4 Missing / Partial Start / Stop Date of Concomitant Medications

For COVID-19 vaccines missing/partial dates will be imputed as follows:

- Completely missing dates will be imputed using 01JAN2021
- If month and day are missing then imputed using 01JAN of the year
- If only day is missing then imputed using the first of the month.

Controlled Quality Management Document		
	Sponsor:	Veru Inc.
	Protocol Number:	V3011902
STATISTICAL ANALYSIS PLAN. PHASE 2-3-4		

If reported COVID-19 vaccine was a single shot then missing end date will be set to equal to start date.

For other concomitant medications missing and partial start and stop date will be imputed for analysis purposes as follows.

Partial or missing stop date will be imputed as follows:

If the stop date is completely missing and the event has resolved, or the subject has stopped taking the concomitant medication, the stop date will be imputed as the date of the subject's last clinic visit in the study.

- If only the year is known, the stop date will be imputed as “31-Dec” of that year or as the date of the subject's last clinic visit in the study if in the same year.
- If the month and year are known, the stop date will be imputed as the last day of that month unless the stop date corresponds to the same month as the subject's last clinic visit in which case the date of subject's last clinic visit in the study will be used instead.

Missing start date will be imputed as follows:

- If the stop date occurs on or after the start of study drug or the event / concomitant medication is ongoing, the start date will be imputed as the date of the first dose of study drug.
- If the stop date occurs before the start of study drug, the start date of the event / concomitant medication will be imputed as the subject's screening date or the stop date of the event / concomitant medication whichever the earlier.

Partial start date (year present, but month and day missing)

- If the stop date occurs on or after the start of study drug or the event / concomitant medication is ongoing, and the year is the same as the year of first dosing the start date will be imputed as “01-Jan” of the same year or the date of the first dose of study drug whichever is latest. If the year is different from the year of first dosing “01-Jan” will be used.
- If the stop date occurs before the start of study drug, the start date of the event / concomitant medication will be imputed as the “01-Jan” of the same year.

Partial start date (month and year present, but day missing)

- If the stop date occurs on or after the start of study drug or the event / concomitant medication is ongoing, the start date will be imputed as the first day of the same month and

Controlled Quality Management Document	
	Sponsor: Veru Inc.
	Protocol Number: V3011902
STATISTICAL ANALYSIS PLAN. PHASE 2-3-4	

year unless this partial start date is in same month as the first dose of study drug in which case the date of first dose of study drug will be used.

- If the stop date occurs before the start of study drug, the start date will be imputed as the first day of the month and year of the partial stop date.

If the start time is missing it will be imputed only in the case where the start date of the concomitant medication / event corresponds to the date of the first dose of study drug. The time will be imputed as the same time as the first dose of study drug. In all other cases the time will not be imputed.

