## **8.0 STUDY PROCEDURES**

### **8.1 Screening**

Potential subjects will be screened for this study in the 3 days prior to enrollment. The following activities will be conducted at screening:

1. Signed informed consent and HIPAA form (or legal documents as directed based on the region outside of the United States) will be obtained prior to any study-specific procedures and a copy of the signed consent form will be given to the subject.
2. Assess subject eligibility for inclusion into this study based on protocol inclusion/exclusion criteria.
3. Pregnancy test (women of childbearing potential only)
4. Medical history will be obtained, including diagnosis of COVID-19 infection (date of diagnosis), details and dates of treatments received, documentation of symptoms related to COVID-19 infection, and COVID-19 vaccination status.
5. WHO Ordinal Scale score assessment
6. The use of any medications will be recorded. This will include medications currently being taken and those taken since COVID-19 symptoms started. Over-the-counter (OTC) medications as well as medications taken on an as-needed basis (PRN) should be recorded.
7. Vital signs (temperature/pulse/supine, if possible, blood pressure)
8. SpO2 level (%)

9. Physical examination including height and weight
10. Electrocardiogram- 12 lead (single)
11. Clinical Laboratory Tests
  - Hematology ([Appendix A](#))
  - Serum chemistry ([Appendix A](#))
  - Urinalysis

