### **8.12 Concomitant Medications and Concomitant Therapies**

Any medication (including OTC medications) taken by a subject within 30 days prior to the Screening Visit and during the course of the study and the reason for use of the medication will be recorded on the eCRF. Upon entering the study, each subject will be instructed to report the use of any medication (including OTC medications) to the investigator.

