14.2.1.11	Proportion of Subjects Alive by Region, Country and Site, and Visit ITT Set	IP	14.2.1.1
14.2.1.12	Logistic Regression for Proportion of Subjects Alive by Region and Visit ITT Set	Stat IP	14.2.1.2
14.2.1.13	Proportion of Subjects Alive by Standard of Care and Visit ITT Set	IP	14.2.1.1
14.2.1.14	Logistic Regression for Proportion of Subjects Alive by Standard of Care and Visit ITT Set	Stat IP	14.2.1.2

	
	
	
	

Controlled Quality Management Document		
	Sponsor:	Veru Inc.
	Protocol Number:	V3011902

Table Number	Table Title	Validation Method	Shell Number (if repeat)
14.2.1.15	Proportion of Subjects Alive by WHO Ordinal Scale at BL and Visit ITT Set	IP	14.2.1.1
14.2.1.16	Logistic Regression for Proportion of Subjects Alive by WHO Ordinal Scale at BL and Visit ITT Set	Stat IP	14.2.1.2
14.2.1.17	Proportion of Subjects Alive by Vaccination Status (All Vaccinated (at Least One Shot) vs. All Unvaccinated) and Visit ITT Set	IP	14.2.1.1
14.2.1.18	Proportion of Subjects Alive by Vaccination Status (All Vaccinated with US Acceptable Vaccine vs. the Rest of the Population) and Visit ITT Set	IP	14.2.1.1
14.2.1.19	Proportion of Subjects Alive by Vaccination Status (All Vaccinated with at Least One Shot within 6 Months of the First Dose on V3011902 vs. the Rest of the Population) and Visit ITT Set	IP	14.2.1.1
14.2.2.1	Proportion of Subjects Alive and Free of Respiratory Failure by Visit ITT Set	IP	14.2.1.1
14.2.2.2	Logistic Regression for Proportion of Subjects Alive and Free of Respiratory Failure by Visit ITT Set	Stat IP	14.2.1.2
14.2.3.1	Descriptive Statistics for Days in Intensive Care Unit (ICU) - Death Assigned to Worst Possible Outcome ITT Set	IP	
14.2.3.2	Analysis of Covariance (ANCOVA) for Days in Intensive Care Unit (ICU) - Death Assigned to Worst Possible Outcome ITT Set	Stat IP	

Controlled Quality Management Document		
	Sponsor:	Veru Inc.
	Protocol Number:	V3011902

Table Number	Table Title	Validation Method	Shell Number (if repeat)
14.2.3.3	Descriptive Statistics for Days in Intensive Care Unit (ICU) by Region - Death Assigned to Worst Possible Outcome ITT Set	IP	14.2.3.1
14.2.3.4	Analysis of Covariance (ANCOVA) for Days in Intensive Care Unit (ICU) by Region - Death Assigned to Worst Possible Outcome ITT Set	Stat IP	14.2.3.2
14.2.3.5	Descriptive Statistics for Days in Intensive Care Unit (ICU) by Standard of Care - Death Assigned to Worst Possible Outcome ITT Set	IP	14.2.3.1

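### For vaccinees whose deciding COVID-19 shot is undated or recorded only as 2021, the SAP's date imputation lets first-dose date alone decide the 6-month vaccination subgroup

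*SAP*

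**What the plan says.** SAP 6.2.4 gives COVID-19 vaccines their own rules for incomplete dates. With no date at all: "Completely missing dates will be imputed using 01JAN2021". With only the year: "If month and day are missing then imputed using 01JAN of the year". With month and year: "If only day is missing then imputed using the first of the month". SAP 6.2.3 lets other eCRF data override these rules, and keeps imputed dates out of the subject listings.

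SAP 6.11.3 plans that "similar analysis to primary analysis will be performed in subgroups for region, standard of care, WHO Ordinal Scale at baseline and vaccination status". SAP 11.1 lists three vaccination splits of the proportion alive. Table 14.2.1.17 is by any shot, Table 14.2.1.18 is by type of vaccine, and Table 14.2.1.19 is by timing: "All Vaccinated with at Least One Shot within 6 Months of the First Dose on V3011902 vs. the Rest of the Population". Only the last needs a vaccination date. No category for unknown timing and no sensitivity check is given for it.

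Protocol 8.1 collects, under medical history, "documentation of symptoms related to COVID-19 infection, and COVID-19 vaccination status". Protocol 8.12 records medication "taken by a subject within 30 days prior to the Screening Visit and during the course of the study". The SAP amendment log shows that the vaccine rule was added in version 5.0 (30 June 2022) as a clarification during output production, in a log of changes made before database lock.

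**The concern.** The timing table asks whether mortality results look the same in recently vaccinated subjects as in everyone else. That needs the interval from shot to first study dose. When the shot date is missing, the rule supplies one fixed calendar date, so the only quantity left that varies between such subjects is the date of first dose. Their class then carries information about when they enrolled and none about when they were vaccinated. After the switch date the error also runs one way: truly recent vaccinees leave the recent group and none enter it.

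Incomplete dates are plausible. Screening asks for vaccination status, and the medication look-back of 30 days is much shorter than the 6 months that the table needs. At stake is the reading of one planned mortality subgroup table. If many records are affected, a difference between its two parts could partly reflect enrolment period.

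**Working it through.** There is no stated figure in the plan to reproduce here; the check is calendar arithmetic plus one labelled assumption.

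**Inputs**
- Imputed dates: SAP 6.2.4.
- Cut-off: 6 months before first dose, from the title of Table 14.2.1.19. The SAP does not define 6 months in days. I use calendar months for the switch date and 182 days in the formulas, which moves the switch by one day.
- Protocol versions: 1.0 on 8 March 2021, 3.0 on 12 May 2021 and 7.0 on 18 March 2022 (SAP title page).
- Recruitment expected within 9 months (Protocol 9.7.1).
- Actual enrolment dates are not given, so the windows below are assumptions.

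**Step 1: the switch date.** 1 January 2021 + 6 months = 1 July 2021. An undated or 2021-only vaccinee first dosed on or before 1 July 2021 is always within 6 months. From 2 July 2021 such a subject is never within 6 months.

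**Step 2: which records are affected**
- Full date: never.
- Another shot dated inside the window: never, since one shot suffices.
- Year-only 2022, first dose by 30 June 2022: correct. The cut-off for 30 June 2022 is 30 December 2021, so 1 January 2022 and every later date count as recent.
- Month and year known: the imputed date is at most 30 days early, so an error needs a true date within about 30 days of the cut-off.
- No date, or 2021 only, first dose after 1 July 2021: always placed outside the window.

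**Step 3: error at a given first-dose date.** Assume true shot dates uniform from 1 January 2021 to first dose, and let t be the days from 1 January 2021 to first dose. For undated records with t > 182, the share truly within 6 months is 182/t, and the rule calls none of them recent.

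| First dose | t | 182/t |
|---|---|---|
| 1 Oct 2021 | 273 | 67% |
| 1 Jan 2022 | 365 | 50% |
| 1 Mar 2022 | 424 | 43% |

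For t ≤ 182 the rule is right under this assumption.

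**Step 4: error over an enrolment window.** With first doses spread evenly from t1 to t2, where t1 < 182 < t2:

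share misclassified = 182 × ln(t2/182) / (t2 − t1)

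- 8 March to 8 December 2021 (t1 = 66, t2 = 341): 182 × 0.628 / 275 = 114.3/275 = 42%.
- 12 May 2021 to 18 March 2022 (t1 = 131, t2 = 441): 182 × 0.885 / 310 = 161.1/310 = 52%. Here the rule labels (182 − 131)/310 = 16% as recent, while 16% + 52% = 68% truly are.
- As a further variation, 12 May 2021 to 12 February 2022 (t2 = 407): 182 × 0.805 / 276 = 146.5/276 = 53%.

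**Step 5: without the uniform assumption.** If no shot predates 1 January 2021, errors can arise only after the switch. The share misclassified then lies between 0 (every late-dosed undated vaccinee had an old shot) and the share of the window after the switch (every one had a recent shot). That upper limit is (341 − 182)/275 = 58% for the first window and (441 − 182)/310 = 84% for the second.

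All these percentages are of undated records, not of the trial population.

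**The case against.** The strongest objection is that very little depends on this.

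- **Reach.** Table 14.2.1.19 is one of three vaccination splits, and the other two need no date. SAP 11.1 lists it as a table of proportions with no matching regression, unlike region, standard of care and WHO score. It lies outside the primary analysis and the Holm procedure. This stands.
- **Frequency.** The number of incomplete dates could be close to zero. The 30-day look-back concerns medications, while vaccination status sits under medical history with no stated limit. Since SAP 6.2.4 handles vaccine start and end dates, the eCRF evidently holds them. This stands too: incomplete dates are plausible but not shown.
- **Defensible convention.** After 1 July 2021 the recent group admits only subjects with sufficient dating of a recent shot. That keeps the group clean, but it does not repair the other part of the split, and the table does not tell its reader.
- **Override.** SAP 6.2.3 lets other eCRF data prevail. It cannot supply a date that nobody recorded.

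Three stronger readings are tempting, and the documents do not support them.

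1. A reader might infer that enrolment date decides the whole subgroup. It does so only for vaccinees whose deciding shot is undated or 2021-only.
2. A reader might infer that recent vaccinees contaminate a control group and bias the treatment effect. The remaining subjects form the other subgroup, not the placebo arm, and by its title that subgroup already mixes unvaccinated subjects with earlier vaccinees. VERU-111 is compared with placebo inside each part, and nothing links an incomplete date to the randomized arm.
3. A reader might infer that the late addition was driven by results, or that FDA asked for this particular split. The log places the change before database lock, and its version 4.0 entry records an FDA request for subgroup analyses of the primary endpoint without naming the 6-month split.

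**Conclusion.** The point holds in a limited form. For vaccinees whose deciding shot is undated or recorded only as 2021, membership of the 6-month subgroup depends on first-dose date alone, and the SAP offers no unknown-date class. Under uniform true dates, roughly 42% to 52% of undated records would be misclassified in the two main windows. The figure rests on that assumption and on assumed enrolment windows. The number of affected records is unknown, so the effect on the table may be small.

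The consequence is a mislabelled secondary, descriptive mortality subgroup, tied partly to enrolment period. The primary analysis and Tables 14.2.1.17 and 14.2.1.18 are untouched. The contrast between the two parts of the split may be blurred; the randomized comparison within each is not biased by this alone. This is an inexpensive improvement and not a threat to the trial's conclusions.

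**What to change.** For Table 14.2.1.19 only, replace the imputed date with a rule based on what was recorded:

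- Classify a vaccinee as within 6 months, or not, only if every date compatible with the record falls on the same side of the cut-off. One shot that is certainly recent settles the class.
- State the earliest vaccination date regarded as possible, because that decides wholly undated records in subjects dosed early.
- Put the remaining vaccinees in a separate row, vaccinated with date unknown, by treatment group.
- As a check, show the table with that row allocated entirely to the recent group and then entirely to the other.

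Listings need no change, since SAP 6.2.3 already shows dates as recorded. The cost is a short addition to the SAP, one table row and two check displays; the two classified subgroups become slightly smaller. If few records are affected, the new row shows it.
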